5. Women of childbearing potential should be protected from pregnancy throughout the study (relevant for long-term use of ticagrelor). Suitable methods of contraception, in this case, include hormonal contraceptives, barrier methods, or complete withdrawal – as long as it is consistent with the patient's lifestyle.

Exclusion criteria

1. Contraindications to antiplatelet therapy with ticagrelor/cangrelor:
 - Recent (< 6 months) major bleeding,
 - Recent (< 1 month) major surgery/injury,
 - History of intracranial hemorrhage,
 - History of Stroke/TIA,
 - Known ticagrelor/cangrelor intolerance,
 - Severe hepatic impairment,
 - Co-administration of potent CYP3A4 inhibitors (e.g., ketoconazole, clarithromycin, nefazodone, ritonavir, and atazanavir).

2. Administration of a loading dose of oral P2Y₁₂ inhibitor before admission (clopidogrel ≥ 300 mg, ticagrelor 180 mg, prasugrel 60 mg).
3. Need for concomitant chronic anticoagulant treatment due to atrial fibrillation, artificial valve, thromboembolic disease, etc.

Study endpoints

Primary endpoint – laboratory

- Comparison of the effect of parenteral cangrelor with the recommended crushed ticagrelor treatment on periprocedural ADP-activated platelet aggregation; the periprocedural rate of onset and the proportion of patients who achieve effective* P2Y₁₂ platelet receptor inhibition defined by a Platelet Reactivity Index (PRI) value at the end of percutaneous coronary intervention.

**Platelet Reactivity Index (PRI) less than 50% as measured by the vasodilator-stimulated phosphoprotein (VASP) phosphorylation flow cytometric assay*

Primary endpoint – clinical

- Comparison of the effect of parenteral cangrelor with the recommended crushed ticagrelor treatment on the incidence of major cardiovascular events 30 days after enrollment in the study. The primary clinical endpoint is a composite of all-cause death, myocardial infarction, or stroke* within 30 days, expressed as a proportion of patients with any of these events. The primary clinical endpoint is non-inferiority, and if this is met, then superiority will be tested.

**Ischemic stroke (intracranial hemorrhage assessed as a BARC 3c bleeding)*

Secondary endpoints

Key secondary efficacy endpoint

- Death, myocardial infarction, urgent revascularization of the infarct-related artery, stent thrombosis, or ischemic stroke within 30 days and one year after study enrollment expressed as a proportion of patients with any of these events.

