- External monitoring is performed by an independent Clinical Research Associate (CRA), which provides regular site monitoring and data validation to ensure data quality and patient safety.
- The Data Safety Monitoring Board (DSMB) periodically reviews accumulated safety data, including adverse event frequencies and severity, to address any unexpected risks promptly.

Substudies

The following substudies are planned:

- Echocardiographic substudy,
- Magnetic Resonance Imaging substudy.

Subgroup analysis

The analysis of the following subgroups is planned in the study:

- Women versus men,
- Patients with prehospital time delay duration 3 hours and longer versus less than 3 hours,
- Patients with and without out-of-hospital cardiac arrest,
- Patients with and without mechanical ventilation,
- Patients with and without mechanical circulatory support (e.g., IMPELLA, ECMO)*
- Patients with and without persistent coma (Glasgow Coma Scale < 8) at admission,
- Patients with and without diabetes,
- Patients with and without obesity,
- Patients who are cigarette smokers versus non-smokers,
- Patients with and without multivessel disease,
- Patients with and without a history of heart failure.

**A time-dependent covariate analysis will be performed instead of standard subgroup analysis to prevent bias due to treatment-dependent selection effects for mechanical circulatory support (MCS), which may occur post-randomization.*

Handling of Post-Randomization Events (MCS)

MCS use will be modeled as time-dependent covariates in survival analyses to avoid bias introduced by post-randomization treatment effects. These covariates will be introduced into the primary and secondary outcome models as follows:

Time-Dependent Covariate Analysis

To accurately account for the influence of MCS on study outcomes, these variables will be modeled as time-dependent covariates within the Cox proportional hazards model:

Primary Model:

- $HR = \beta_1(\text{Treatment}) + \beta_2(\text{Mechanical Ventilation (time-dependent)}) + \beta_3(\text{ECMO (time-dependent)}) + \epsilon$
- This ensures that the estimation of treatment effects is not confounded by patients who deteriorate and need additional support after randomization.

Competing Risks Model (Fine & Gray) for Non-MACE Outcomes:

- If MCS is strongly associated with mortality before the primary endpoint, a competing risks approach will be applied using the Fine & Gray subdistribution hazard model.

Sensitivity Analysis

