Standard descriptive statistics will be employed in the analysis to summarize both categorical and continuous variables. For categorical variables, data will be presented as absolute frequencies (i.e., counts) and relative frequencies (i.e., percentages), clearly representing each category's distribution across the study groups. For continuous variables (including pharma-economic data), the data will be reported either as the median supplemented with the interquartile range (IQR) or the 5th to 95th percentiles range, which captures the central tendency and spread in a non-parametric manner or as the mean supplemented with the standard deviation, which provides a measure of central tendency and variability under the assumption of normal distribution. The choice between median and mean reporting will depend on the distributional properties of the continuous variables. Data visualization will use standard box and whisker plots for continuous variables and bar plots for categorical variables. Relative risks and 95% confidence intervals will be used to describe and visualize the results of endpoint analysis.

The chi-square test will be employed for categorical variables, including the primary and secondary study endpoints and all other relevant categorical data, to assess the statistical significance of observed differences between groups. This test will evaluate whether the observed frequencies in different categories deviate from what would be expected under the null hypothesis. The Mann-Whitney U test will be applied for continuous variables, as it is a robust non-parametric alternative to the t-test, particularly useful when the assumption of normality is not met. This test will determine whether there are statistically significant differences in the distribution of continuous variables between the study arms. The non-inferiority scenario will be assessed using a one-sided Z-test with a non-inferiority margin of 1%.

To ensure comparability among centers, the data for analyzing maximum values of high-sensitivity cardiac troponin will be presented as the ratio of the maximum value within seven days to the reference value for myocardial infarction at a specific center.

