A p-value of 0.05 will be adopted as the threshold for determining statistical significance across all analyses. All statistical analyses will be conducted in strict accordance with the regulatory guidelines outlined in the E9 Statistical Principles for Clinical Trials document published by the U.S. Food and Drug Administration (FDA) under the reference FDA-1997-D-0508. These guidelines ensure that the statistical methods employed adhere to established clinical trial data analysis standards, ensuring rigor, reproducibility, and validity of findings.

Variables and tables will be presented in the order in which the sections are shown in the eCRF. Parameters recorded in more than one SI unit (e.g., lab units) will be converted into a single SI unit as appropriate.

Description of patients' characteristics

Prior to the analysis of the primary and secondary endpoints, the treatment groups (or any groups in subgroup analyses) will be compared about the following patients' characteristics:

- Demographics: age, sex, body weight, body mass index (BMI), obesity, and cigarette smoking.
- Characteristics of AMI at admission: type of acute myocardial infarction (STE- or NSTEMI), mechanical ventilation upon admission.
- Time delay: from symptoms to hospital, from symptoms to reperfusion.
- Out-of-hospital cardiac arrest: cardiopulmonary resuscitation before admission, first documented rhythm, time to return of spontaneous circulation (ROSC) (min), external cardiac massage - before admission, on admission, overall duration, mechanical ventilation, regulation of body temperature, target value.
- Patient's status at the time of admission: blood pressure - left arm systolic/diastolic (mmHg), blood pressure - right arm systolic/diastolic (mmHg), pulse rate (BPM), cyanosis, mydriasis, transient mydriasis, deep unconsciousness without prior treatment with hypnotics.
- Treatment with vasopressors and/or inotropic agents, noradrenaline, adrenaline, dopamine, dobutamine, another vasopressor agent, another inotropic agent.
- Analgosedation: analgosedation, opioid (morphine, fentanyl, sufentanil), benzodiazepine (midazolam, diazepam, other), propofol, another analgosedation method.

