The analysis of the primary and secondary endpoints in the complete study population assumes a balanced distribution of potentially confounding factors between the study arms, which is expected to be achieved through randomization. Considering this assumption, no prior planned multivariate adjustment for the confounding variables will be conducted in the initial analysis of the primary endpoints. However, despite this, further exploratory analyses will incorporate both univariate and multivariate models, such as logistic regression and Cox proportional hazards models, to evaluate the potential influence of specific patient characteristics on the occurrence of the endpoints. This approach will provide a more detailed understanding of how individual baseline factors may affect study outcomes. Additionally, time-to-event data will be visualized using the Kaplan-Meier methodology, allowing for an informative representation of the temporal aspects of endpoint occurrences. Time to the event will be computed from the date of randomization and the date of the analyzed event or the date of last contact in the case of censored patients.

For subgroup analyses, where confounding factors may exhibit an unbalanced distribution across the study arms, they will be incorporated into the multivariate logistic regression models. This will allow for appropriate adjustment for these confounders, providing a more accurate estimation of the association between treatment effects and study endpoints in the presence of imbalances. By accounting for such factors, the analysis will enhance the robustness and validity of the conclusions drawn regarding the study outcomes within the specified subgroups.

Safety analysis

This phase IV clinical trial focuses on observing and comparing the use of approved medicinal products as part of standard clinical practice. Information regarding side effects will neither be actively collected nor evaluated.

Hospitalizations and life-threatening conditions, which are prerequisites for study enrollment, are not categorized as serious adverse events (SAEs). The investigator will perform causality assessments, and immediate reporting of adverse events unrelated to the study will not be required.

In routine clinical practice, cardiogenic shock has a mortality rate of over 50%. Deaths unrelated to the study will be summarized and included in annual study reports.

References

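### The 0.05 significance threshold covers about 25 secondary comparisons with no testing order, no gate on the primary clinical result and no exploratory label

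*SAP*

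**What the plan says.** The threshold is in the SAP's Statistical analysis section: "A p-value of 0.05 will be adopted as the threshold for determining statistical significance across all analyses". That section also says which comparisons are tested. For proportions: "The chi-square test will be employed for categorical variables, including the primary and secondary study endpoints and all other relevant categorical data". For continuous outcomes it names the Mann-Whitney test and adds: "This test will determine whether there are statistically significant differences in the distribution of continuous variables between the study arms".

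Study endpoints divides the outcomes into primary, key secondary (one efficacy, one safety) and other secondary. The key secondary efficacy endpoint is "Death, myocardial infarction, urgent revascularization of the infarct-related artery, stent thrombosis, or ischemic stroke within 30 days and one year after study enrollment". No order between the two time points is given. The only sequence of tests in the SAP lies within the primary clinical endpoint: "The primary clinical endpoint is non-inferiority, and if this is met, then superiority will be tested".

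The Subgroup analysis section opens with "The analysis of the following subgroups is planned in the study" and lists eleven factors. Mechanical circulatory support is then moved to a time-dependent model, which leaves ten standard subgroups. The word exploratory is applied to the models in Additional analyses, where "further exploratory analyses will incorporate both univariate and multivariate models, such as logistic regression and Cox proportional hazards models". It is not applied to the secondary endpoints or to the subgroups.

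**The concern.** Read together, these statements allow each secondary comparison to be called statistically significant at 0.05 on its own, whatever the primary clinical endpoint shows. Naming a tier key signals importance, but it does not say when a claim may be made, in what order, or at which time point.

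At stake is how secondary results will be read. If the primary clinical endpoint is missed, nothing in the SAP prevents a secondary result with p below 0.05 from being presented as an established effect. A reader of the trial report could not tell a pre-ranked finding from one that stands out among some 25. The primary analysis itself is not affected. The point is also separate from how alpha is shared between the two primary endpoints, and it would remain if that were settled.

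**Working it through.** **1. The alpha level in use.** The SAP states no overall error rate for the secondary endpoints, so there is no such figure to reproduce. Its superiority sample size shows how 0.05 is used. With 50% against 38%, power 0.8 and two-sided 0.05, n per arm = [1.960·√(2·0.44·0.56) + 0.842·√(0.50·0.50 + 0.38·0.62)]² / 0.12² = 267.4, rounded up to 268. The total is 536, as stated. Two-sided 0.05 is therefore used for each secondary test below.

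**2. Count of distinct secondary comparisons (Study endpoints).**

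| Endpoint | Comparisons |
|---|---|
| Key efficacy composite, 30 days and one year | 2 |
| BARC ≥ 3B bleeding, 30 days and one year | 2 |
| Composite including major bleeding, both times | 2 |
| Cardiovascular composite, both times | 2 |
| Death, infarction and stroke separately, both times | 6 |
| Heart failure, both times | 2 |
| Cardiovascular death, both times | 2 |
| Stent thrombosis; delayed bypass surgery; PRI at 1 hour | 3 |
| Support duration; ICU stay; hospital stay; peak troponin | 4 |
| **Total** | **25** |

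The 30-day bleeding line that recurs among the other secondaries is counted once. Subgroups and repeats in the ITT and per-protocol populations are left out.

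**3. Chance of at least one nominally significant result when there is no effect.** If the tests are independent, the chance in either direction is 1 − 0.95²⁵ = 0.72, and in favour of cangrelor 1 − 0.975²⁵ = 0.47. The endpoints overlap, so I also took normal test statistics with a common correlation ρ. With c = 1.96, the two-sided chance is 1 − ∫[Φ((c − √ρ·s)/√(1−ρ)) − Φ((−c − √ρ·s)/√(1−ρ))]²⁵ φ(s) ds. Dropping the second Φ term gives the chance in favour of cangrelor.

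| Assumed ρ | Either direction | Favouring cangrelor |
|---|---|---|
| 0 | 0.72 | 0.47 |
| 0.3 | 0.61 | 0.32 |
| 0.5 | 0.47 | 0.23 |
| 0.8 | 0.24 | 0.12 |

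The expected number of false positives is 25 × 0.05 = 1.25 in either direction at any correlation.

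**4. The key secondary efficacy endpoint alone.** Events by 30 days are nested in events by one year. For cumulative proportions p₁ and p₂ the correlation of the two test statistics is r = √[p₁(1 − p₂) / (p₂(1 − p₁))]. The proportions below are assumed.

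| p₁ / p₂ | r | Either direction | Favouring cangrelor |
|---|---|---|---|
| 50% / 55% | 0.905 | 0.070 | 0.035 |
| 50% / 60% | 0.816 | 0.077 | 0.038 |
| 52% / 65% | 0.764 | 0.080 | 0.040 |

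**5. Primary superiority missed, key secondary efficacy nominally better at either time.** Every component of the primary composite is also in the key composite, so the two are strongly correlated. With nested normal statistics and assumed rates of 45% to 50% for the primary and 50% to 52% (30 days) and 60% to 65% (one year) for the key composite, the chance is about 0.02.

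**The case against.** The strongest reply is that the risk of a false claim of benefit is smaller than two-sided figures suggest. That stands. Results favouring cangrelor are about half the two-sided figures. For the key efficacy endpoint alone the chance is 0.035 to 0.040, and the case of a missed primary with a favourable key secondary is about 0.02. The key endpoint's two time points still need an order, but they are not where most of the risk lies.

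Second, the SAP does rank its endpoints in tiers, and it already plans relative risks with 95% confidence intervals. That also stands; what is missing is a testing order, a gate and a label.

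Third, secondary endpoints are conventionally taken as supportive, and the protocol, not at hand, may contain a hierarchy. This does not remove the point. The SAP does not leave the matter open: it states a threshold for all analyses, and a hierarchy in the protocol would conflict with that sentence.

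Fourth, bleeding is counted in the 25 although the fix leaves it outside the sequence. Leaving out its two comparisons changes little: for 23 independent tests, 1 − 0.95²³ = 0.69 in either direction and 1 − 0.975²³ = 0.44 favouring cangrelor.

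Three stronger readings are not supported:

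- A reader might infer that a false significant secondary result is likely. Whether the chance exceeds one half depends on correlations that the SAP does not give; at ρ = 0.5 it is 0.47.
- A reader might infer that the Interim analysis section promises a 5% error rate for secondary claims. That section only justifies having no interim looks.
- A reader might want to attach a false-positive rate to the subgroups. The SAP describes forest plots and adjusted models but does not specify a test within each subgroup level, so no such rate follows from it.

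**Conclusion.** The point holds as a defect of the stated significance rule. Applied as written, the rule lets about 25 secondary comparisons each be declared significant, with no gate, order or exploratory label. With no true effect, the chance of at least one nominally significant result is about 0.24 to 0.72 in either direction, and about 0.12 to 0.47 in favour of cangrelor. These ranges assume two-sided 0.05 per test and a common correlation between 0.8 and 0; they are not properties that the SAP states. Each single test keeps its nominal 5%; what is uncontrolled is the set. The matter should be corrected, but it does not threaten the primary analysis.

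**What to change.** Replace the sentence on the 0.05 threshold with text such as:

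*The 0.05 threshold for statistical significance applies to the primary endpoints and then, in a fixed sequence gated on the primary clinical endpoint, to the key secondary efficacy endpoint at 30 days and, if significant, at one year. The key secondary safety endpoint (BARC ≥ 3B bleeding) is outside this sequence and is reported at both time points with unadjusted 95% confidence intervals and p-values. All other secondary endpoints and all subgroup analyses are exploratory, reported as estimates with 95% confidence intervals and nominal p-values, without claims of significance.*

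The text should also say which primary clinical test, non-inferiority or superiority, opens the gate. The sponsor may choose another gate or order, provided it is fixed before unblinding. A fixed sequence keeps 0.05 at each step, so alpha is not divided. Naming bleeding explicitly keeps the key safety endpoint from falling under the exploratory label, so detection of harm is not weakened.

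The change needs no new patients, data or analyses. Its cost is that a nominally significant lower-ranked secondary or subgroup result can no longer be presented as confirmed.

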Data management

Data security within the study database is of key importance. Data of individual project are stored in a database system based on a modified version of the TrialDB web-based system for the data collection, which was developed by the Institute of Biostatistics and Analyses, Faculty of Medicine, Masaryk University, Czech Republic, on the base of TrialDB system (Brandt et al. I, 2003). This online system has changed its layout and structure, making data entry even more convenient, while maintaining security measures at the same level. The system is designed as a robust foundation for collecting substantial amounts of data in clinical trials and/or clinical registries. It is fully customized to the structures of individual projects. The online application is accessible to users through a web browser. The security of individual records within the database is guaranteed via de-identified data collection. The identity of each patient is replaced with an identification number (ID), which does not allow any backward identification of that person. The unequivocal identification of a patient is only known to the attending physician or authorized health care professional.

Randomization

The patient will be randomized after the informed consent form has been signed. As this is an acute condition, an abbreviated version of the informed consent form (one-page A4 format) will be available to the patient following applicable law. After the patient's condition has stabilized, a full version of the informed consent form will be presented to the patient (consent to continue in the clinical trial). The full and abbreviated versions of the informed consent form are attached to the final version of the protocol.

An online database system (TrialDB) provides randomization for data collection. After entering basic patient data (age, gender, body weight, type of acute myocardial infarction, and mechanical ventilation upon admission), a study arm inclusion and a randomization code are generated based on a predefined randomization scheme. The patients are randomized in a 1:1 allocation ratio using random permuted blocks, with the size of block four stratified by the center.

Unblinding

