The dual approach of automated electronic validation through TrialDB and manual verification by a monitor and investigating team aims to uphold the highest data quality standards, ensuring that the data submitted for analysis are accurate and reliable, thereby enhancing the overall integrity of the study findings. The final validation of endpoints is provided by the endpoint adjudication committee and approved by its chairperson. Each endpoint is evaluated by two independent experts, with a third expert resolving any disagreements, ensuring robust and unbiased endpoint classification.

Statistical analysis

Statistical software and responsibilities

The data will be reviewed and statistically processed in the statistical analysis center: Institute of Biostatistics and Analyses, Faculty of Medicine, Masaryk University, Brno, [name], MS.c. Ph.D. The analysis will be computed using SPSS 27.0.1 (IBM Corporation, 2021).

Handling of missing values and outliers

Missing values are subject to validation procedures and will be communicated with study sites using lists of detected problems. If correction of missing values is not possible, no imputation of missing values will be performed. The presence of outliers will be evaluated using visual inspection of the continuous variable distribution; detected outliers will be removed from the statistical computations.

Interim analysis

No interim analysis is planned for this study; the decision can be justified as follows:

Reduction of Type I Error: Conducting interim analyses introduces the risk of inflating the Type I error rate. By avoiding interim analyses, the SAP maintains the integrity of the statistical significance threshold (e.g., a p-value of 0.05).

Pragmatic Feasibility: Given the acute nature of myocardial infarction with cardiogenic shock, the timeline for endpoint occurrences (30 days for primary endpoints) is relatively short, reducing the value of interim results for decision-making purposes.

Cost and Logistical Considerations: Implementing interim analyses would require additional resources, such as re-randomization schemes, database locks, and independent review committees, which are unjustified given the study's endpoints and anticipated outcomes timeline.

To mitigate risks associated with the absence of interim analysis:

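### A Cox model with post-randomization covariates is worded as primary for the 30-day composite, while the planned primary test leaves baseline data unused

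*SAP*

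**What the plan says.** All references are to the SAP.

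- **Endpoint.** Under Primary endpoint – clinical, the composite of death, myocardial infarction or stroke is taken "within 30 days, expressed as a proportion of patients with any of these events".
- **Tests.** The second section headed Statistical analysis assigns the chi-square test to the primary and secondary endpoints. Non-inferiority gets a one-sided Z-test with a margin of 1 percentage point.
- **Adjustment.** Additional analyses expects randomization to balance confounders and therefore says "no prior planned multivariate adjustment for the confounding variables will be conducted in the initial analysis of the primary endpoints". Baseline factors appear only in later exploratory models.
- **Data available before allocation.** Under Randomization, patients are allocated "using random permuted blocks, with the size of block four stratified by the center". Age, sex, body weight, infarction type and ventilation on admission are entered first.
- **Post-randomization support.** A footnote under Subgroup analysis says of mechanical circulatory support (MCS): "A time-dependent covariate analysis will be performed instead of standard subgroup analysis". Handling of Post-Randomization Events (MCS) goes further: "These covariates will be introduced into the primary and secondary outcome models as follows". Time-Dependent Covariate Analysis adds that "these variables will be modeled as time-dependent covariates within the Cox proportional hazards model", labels as primary an equation with treatment, ventilation and ECMO, and gives the reason: "This ensures that the estimation of treatment effects is not confounded by patients who deteriorate and need additional support after randomization".

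**The concern.** There are two separate problems, both confined to the clinical composite. Neither extends to the laboratory endpoint.

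**Which model is primary, and why.** Two sections describe an unadjusted comparison of proportions. A third puts post-randomization covariates into the primary outcome model. If the third were followed, the estimate would no longer be the total effect of randomized treatment. Support started after randomization may itself be affected by treatment. Conditioning on it can remove part of a true effect or, where unmeasured severity drives both support and events, create an apparent one. The SAP's reason runs the other way, since it presents the adjustment as protection against confounding. A reader could then take the Cox estimate as the more trustworthy one even if it were only supplementary. The model also yields a hazard ratio, for which the SAP sets no non-inferiority margin.

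**Precision left unused.** Expected balance justifies the unadjusted test as unbiased. It is no reason to ignore prognostic data that are recorded for every patient before allocation. This is a loss of efficiency, not an error.

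**Working it through.** **1. The plan's own figures.** Inputs are from the two power-analysis sections for the clinical endpoint.

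- Superiority, 50% vs 38%, two-sided 0.05, power 0.80, pooled null variance: n per arm = [1.960·√(2·0.44·0.56) + 0.842·√(0.50·0.50 + 0.38·0.62)]² / 0.12² = 267.4, so 268 per arm, 536 in total, as stated.
- Non-inferiority, 50% vs 40%, margin 1 point, one-sided 0.05: n per arm = (1.645 + 0.842)²·2·0.45·0.55 / 0.11² = 252.9, so 253 per arm, 506 in total, as stated.

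Both sizes are those of unadjusted comparisons, so the planned tests match the design.

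**2. Value of baseline adjustment.** The SAP gives no prognostic strength, so R² (the share of outcome variance explained by baseline data) is assumed. The variance of the risk difference is multiplied by (1 − R²) at 268 per arm. Superiority power is Φ[(0.12 − 1.960·SE₀·√(1−R²)) / (SE₁·√(1−R²))], with SE₀ = √(2·0.44·0.56/268) and SE₁ = √((0.25 + 0.2356)/268). Non-inferiority power is Φ[0.11/(SE·√(1−R²)) − 1.645], with SE = √((0.25 + 0.24)/268).

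| Assumed R² | Superiority power | Non-inferiority power | SE at 50% vs 38% (points) | Equivalent patients (536·R²) |
|---|---|---|---|---|
| 0 | 80.1% | 82.3% | 4.26 | 0 |
| 0.02 | 80.9% | 83.0% | 4.21 | 11 |
| 0.05 | 82.1% | 84.0% | 4.15 | 27 |
| 0.10 | 84.1% | 85.7% | 4.04 | 54 |
| 0.17 | 86.9% | 88.1% | 3.88 | 91 |

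**3. Simulation of the adjusted estimator.** This used a standardized risk difference, robust standard error, 536 patients, blocks of four within 8 or 15 unequal centres, centres under 20 patients pooled, three covariates plus centre, and 6000 runs. Centre numbers and covariate effects are assumed, as is a between-centre log-odds SD of 0.3 in the R² 0.10 runs.

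- R² 0: superiority power 80.4% to 80.2% (8 centres) and 80.1% to 80.2% (15), within simulation error.
- R² 0.10: 79.8% to 83.8% and 80.3% to 84.4%.
- Non-inferiority at 50% vs 40%, R² 0.10: 81.3% to 85.2% and 81.9% to 85.5%.
- Two-sided size: chi-square 0.044–0.057, adjusted 0.045–0.058. One-sided size at the margin: 0.046–0.049 and 0.048–0.052.
- Centre alone (Cochran-Mantel-Haenszel minus chi-square), at between-centre log-odds SD 0, 0.3 and 0.6: 0.0, +0.3 and +1.5 points (8 centres); −0.3, +0.4 and +1.7 (15).

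**4. Effect of conditioning on support.** All inputs are assumed: a Cox fit on expected counts over 30 days, front-loaded hazards, 40% of controls starting support, a support hazard ratio of 2 or 3, and unmeasured severity with log-hazard 0 or 0.6 on both support and events. The true risks are 50% vs 40%.

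| Share of effect acting through less support | HR without support in the model | HR conditioned on support |
|---|---|---|
| None | 0.73–0.74 | 0.70–0.73 |
| One quarter | 0.73–0.74 | 0.78–0.81 |
| One half | 0.73–0.74 | 0.85–0.91 |

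If treatment changes only the use of support (HR 0.5, 0.7 or 1.43), support has no effect on events, and severity has log-hazard 0.3–0.9, the unconditioned HR is 1.000 and the conditioned HR is 0.935–1.109. A separate logistic illustration had treatment lower MCS use with no direct effect on the outcome. Its total-effect odds ratio of 0.93 became 1.07 after conditioning.

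**5. The margin on the hazard scale.** Under proportional hazards, HR = ln(1 − p − 0.01)/ln(1 − p). At p = 50% this is ln 0.49/ln 0.50 = 1.029. It is 1.040 at 30% and 1.028 at 60%. The fixed 1-point margin therefore has no single hazard-ratio equivalent.

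**The case against.** **On adjustment.** An unadjusted primary test is a legitimate choice, it matches the sample size, and the SAP's remark about balance is sound on its own terms. Multivariable models are already planned as exploratory. The gain cannot be derived from the SAP and may be nil. All of this stands, so this part is an improvement rather than a correction.

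**On the Cox model.** It follows a footnote about subgroups, under a heading about post-randomization events. Its label can be read as the main model within that analysis, since competing-risks and sensitivity analyses follow. A supplementary role is probably what was meant, and nothing in the SAP applies the 1-point margin to a hazard ratio. The larger distortions matter for the primary result only if the model were treated as primary; with no mediation the shift is small. But the intended role has to be inferred against wording that says the opposite, and the statement about confounding is wrong on either reading.

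**On the remedy.** Changing the primary estimator may need a matching protocol change, because the protocol was not available for this review. Whether the estimator runs conveniently in the named SPSS version was not checked. The outlier problem dealt with in the fix arises only once a continuous covariate enters the model. These are costs to plan for and do not remove the contradiction.

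**Conclusion.** The concern holds and should be settled before unblinding.

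The stronger part is the Cox section. Its wording contradicts the proportion endpoint, the planned tests and the no-adjustment rule, and its rationale treats a possible consequence of treatment as a confounder. The size of any bias rests entirely on assumed inputs: negligible to small without mediation, and enough to move a hazard ratio of about 0.74 to as high as 0.91 if half the effect acts through support.

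The weaker part is lost precision. The planned tests are valid. Adjustment would add about 1 to 7 points of superiority power for R² between 0.02 and 0.17, and nothing at R² 0. Centre alone adds about 0 to 2 points. Confidence in the size is moderate at best, because the SAP gives neither prognostic strength nor the number and size of centres.

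**What to change.** Before unblinding:

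1. State that the composite has a single primary analysis, on the risk-difference scale, with baseline covariates only. Label the time-dependent Cox models supplementary and delete the sentence claiming that they prevent confounding. This step is needed whether or not step 2 is adopted.
2. Prespecify a standardized risk difference from logistic regression with robust variance. Adjust for centre and a fixed list of the variables entered before allocation, for example age, ventilation on admission and infarction type. Pool small centres by a fixed rule. Use this for non-inferiority and superiority, which keeps the 1-point margin, and retain the unadjusted Z-test and chi-square test as sensitivity analyses.
3. Handling of missing values and outliers says that "detected outliers will be removed from the statistical computations". State that this does not apply to covariates in the primary model, so that no patient in the analysis population is lost through a covariate value. Otherwise each 1% removed costs about 5 of 536 patients, against a total drop-out allowance of 14 (550 − 536).

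The cost is SAP wording, a little programming, agreement in advance on the covariate list and pooling rule, and alignment with the protocol if it names the primary test. No extra patients or data are needed, and the precision gain may prove small.
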